11.2.4. Demography and Other Baseline Data

Demographic data and subject characteristics at screening/baseline will be listed and summarized by treatment group for all randomized subjects using descriptive statistics.

Past and current medical history will be summarized by treatment group using the system organ class (SOC) as coded using the Medical Dictionary for Regulatory Activities (MedDRA) coding dictionary.

Past medical conditions will be defined as an onset date prior to randomization (Visit 2) and resolved (not on-going) as of Visit 2. Current medical conditions, defined as an onset date on or after the date of randomization (Visit 2) or an onset date prior to randomization (Visit 2) and

unresolved (on-going) as of Visit 2, will be reported separately, but similarly to the past medical conditions. If both a past and a current (on-going) medical condition record are indicated for a condition, the condition will be presented under current medical conditions only.

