11.2.6. Prior/Concomitant Therapy

Any medications or therapy present before the first dose of study medication (Visit 2) will be considered as prior medications. Concomitant medications (medications present while on study medication) will be recorded throughout the study and at early discontinuation. These medications will be coded using the WHO-drug dictionary. The number of subjects from the Safety Population using prior or concomitant medications will be categorized by the WHO-drug category and preferred term, and presented for each treatment group. In any given category (e.g., drug category) a subject will be counted only once.

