11.4.1. Adverse Events

Adverse events will be recorded throughout the study and at early discontinuation. Adverse events and medical conditions will be coded using the Medical Dictionary for Regulatory Activities (MedDRA) coding dictionary. Treatment-emergent adverse events will be defined as those events, which are newly occurring or worsening from baseline. In all cases only treatment emergent adverse events will be summarized.

Treatment-emergent adverse events will be summarized within each treatment group by primary system organ class (SOC) and preferred term. (***NOTE***: In any given category [e.g. body system] a subject will only be counted once.) The incidence rates of TEAEs will be analyzed as described in the SAP. Similar displays will be provided for SAE and prior (conditions ending prior to the first dose of study medication and current (conditions present while on study medication) medical conditions.

Adverse events will further be categorized by severity, relationship to study medication, and action taken. Other information collected will be listed, as appropriate. Any event starting more than 3 days after the final dose of study medication will be excluded from the above tables and only listed, unless the event caused discontinuation.

The proportions of subjects experiencing SAEs and AEs resulting in discontinuation from the study will be summarized by treatment groups.

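### Section 11.2.4 counts conditions that start at or after randomization as current medical history, so a by-arm baseline table can be altered by treatment (minor, descriptive only)

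*SAP*

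**What the plan says.** SAP section 11.2.4 opens with its scope: "Demographic data and subject characteristics at screening/baseline will be listed and summarized by treatment group for all randomized subjects". It then adds that "Past and current medical history will be summarized by treatment group", by system organ class.

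Two categories follow. The past category is limited to the time before treatment: "Past medical conditions will be defined as an onset date prior to randomization (Visit 2) and resolved (not on-going) as of Visit 2". The current category has two limbs. The first reads: "Current medical conditions, defined as an onset date on or after the date of randomization (Visit 2". The second covers conditions with earlier onset that are still present, and the text continues: "unresolved (on-going) as of Visit 2, will be reported separately, but similarly to the past medical conditions". Where a condition has both a past record and a current (ongoing) record, "the condition will be presented under current medical conditions only".

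Two other sections bear on this:

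- Section 11.2.6 fixes the timing of treatment: "Any medications or therapy present before the first dose of study medication (Visit 2) will be considered as prior medications".
- Section 11.4.1 defines the safety events: "Treatment-emergent adverse events will be defined as those events, which are newly occurring or worsening from baseline". It also plans displays of prior and current medical conditions using a different pair of definitions. There, prior means ended before the first dose, and current means present during treatment.

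**The concern.** A condition that begins after randomization cannot describe a patient at entry. The first limb nevertheless puts it in the baseline section and summarizes it by arm. If the drug causes or prevents new conditions, the difference can appear as a difference in medical history. The same condition can also be counted as a treatment-emergent event, because nothing in the documents assigns it to one table only.

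What is at stake is how the table is read. Readers use by-arm history to judge whether the arms were alike at the start, and a table that treatment can change is unreliable for that. The SAP does not state this purpose; it is inferred from the section heading and from the reference to screening/baseline in its first sentence.

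**Working it through.** No arithmetic in the plan applies. The point concerns a classification rule and does not depend on alpha, power, effect size or sample size. The check is to apply the definitions to each kind of condition.

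**Step 1. Timing.** Section 11.2.4 identifies randomization with Visit 2, and section 11.2.6 puts the first dose at Visit 2. A condition caught by the first limb therefore arises essentially on or after treatment.

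**Step 2. Apply both sections to each case.**

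| Condition | Section 11.2.4 | Section 11.4.1 event tables |
|---|---|---|
| Onset before Visit 2, resolved by Visit 2 | Past | No |
| Onset before Visit 2, ongoing, unchanged | Current (second limb) | No |
| Onset before Visit 2, ongoing, worsens on treatment | Current (second limb) | Yes, for the worsening |
| New onset after first dose, up to 3 days after the last dose | Current (first limb) | Yes |
| New onset more than 3 days after the last dose | Current (first limb) | Listed only, unless it caused discontinuation |
| Resolved before Visit 2, recurs on treatment | Depends on how the tie-break is read | Yes |

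The first three rows are sound: baseline status is fixed by what was true at Visit 2. The fourth row is the overlap. The fifth shows that the first limb has no time limit, whereas section 11.4.1 does. The sixth is unclear.

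**Step 3. Look for a rule that removes the overlap.** None was found. No passage excludes first-limb conditions from the history table or shows them separately from second-limb conditions.

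**Step 4. Compare the two sets of definitions.** Section 11.2.4 divides at randomization and counts any later onset as current. Section 11.4.1 divides at first dose and ties current to the treatment period. The two need not give the same table.

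**Step 5. What would determine the size.** Take one system organ class row and assume each patient is counted once in it. Section 11.4.1 states that rule for adverse events; section 11.2.4 does not state it for history. Let *b* be the proportion with an ongoing condition in that class at entry, equal in both arms. Let *r*(T) and *r*(P) be the proportions of the remaining patients in the tradipitant and placebo arms with a new onset recorded as a medical condition. Then

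- row percentage in an arm = *b* + (1 − *b*) × *r*
- false difference between arms = (1 − *b*) × (*r*(T) − *r*(P))

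Where *b* = 1 the false difference is 0. It equals the full difference in recorded onset rates only where *b* = 0. The documents give none of *b*, *r*(T) and *r*(P), so no figure can be stated.

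**The case against.** The strongest reply is that the rule may do little in practice, and that several stronger readings go beyond the text.

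- **Adverse events may never reach this table.** A reader might infer that every new event enters the history table, so that a difference in event rates carries over one for one. The documents do not show this. Section 11.4.1 refers to adverse events and medical conditions as separate items, and the case report form is not available. The formula above also shows that conditions already ongoing at entry dilute the effect. Every randomized patient has gastroparesis, so if the study disease is recorded as history, a row for any current condition would already be near 100% in both arms. This stands: overlap is possible, but its extent is unknown.
- **The past table may be safe.** A reader might infer that the tie-break moves a resolved condition out of past history when it recurs on treatment. The tie-break qualifies the current record as ongoing, which echoes the second limb, so it may only prevent double listing at entry. The text is ambiguous and does not establish the stronger reading.
- **Treatment-emergence is judged elsewhere.** A reader might infer that these conditions would be taken for pre-existing ones. Section 11.4.1 does not refer to the history table, and a first-limb condition by definition has an onset date at or after Visit 2. The documents do not support this inference.
- **The convention may be deliberate.** The section 11.4.1 display suggests an on-treatment view was wanted for safety. That could justify a safety display, but not its place under baseline data.
- **Detail is deferred.** Section 11.2 describes itself as general and leaves full methodology to a separate plan. That plan could correct the rule, but the text here is an explicit definition, not a gap waiting to be filled.

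If the history form closes at Visit 2, the first limb is empty and deleting it costs nothing. If it does not, the table is contaminated. The correction is right in both cases.

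**Conclusion.** The definition is wrong as written, and the point is minor. The first limb lets on-treatment conditions into a by-arm table in the baseline section, where treatment can alter the result and where it can overlap with the treatment-emergent tables.

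The effect is confined to description. Medical history is not a term in the MMRM or the ANCOVA of section 11.3.1, and no test on it is planned, so the primary analysis is untouched. Past and current conditions are reported separately, so the table directly exposed is the current-conditions table.

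The conclusion rests on the literal wording of section 11.2.4, on the first dose being at Visit 2, and on the inference that the table is meant to describe patients at entry. Whether any distortion occurs depends on whether post-randomization onsets are recorded as medical conditions, which the documents do not say.

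**What to change.** 1. In section 11.2.4, delete the first limb of the current-conditions definition. Current conditions are then those with onset before Visit 2 that are ongoing at Visit 2.
2. State that the past/current tie-break uses only records with onset before Visit 2.
3. Report new onsets after first dose as adverse events. Report worsening of a pre-existing condition as an adverse event too, but keep that condition in the baseline history table. Removing it would again make baseline history depend on what happened after randomization.
4. Reconcile the prior/current wording and the cut-points (randomization or first dose) between sections 11.2.4 and 11.4.1. Alternatively, label the section 11.4.1 display as an on-treatment safety display and not baseline data. The cut-point matters because the section 11.2.2 populations allow for patients who are randomized but never dosed.

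The cost is a few sentences, with no change to data collection or trial conduct. Section 11.2 allows changes in statistical methods before database lock to be documented in the SAP without a protocol amendment.

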11.2.5. Study Medication

The number of subjects at each visit will be summarized by treatment group.

The compliance to study medication, as recorded in the CRF, will also be summarized by treatment group. The proportion of subjects who are significantly noncompliant in the double-blind phase will be summarized by treatment groups.

11.2.6. Prior/Concomitant Therapy

Any medications or therapy present before the first dose of study medication (Visit 2) will be considered as prior medications. Concomitant medications (medications present while on study medication) will be recorded throughout the study and at early discontinuation. These medications will be coded using the WHO-drug dictionary. The number of subjects from the Safety Population using prior or concomitant medications will be categorized by the WHO-drug category and preferred term, and presented for each treatment group. In any given category (e.g., drug category) a subject will be counted only once.

11.3. Efficacy Data Analysis

11.3.1. Primary Outcome and Methodology

The primary efficacy outcome measure will be change from baseline to Week 12 (Visit 8) in daily nausea severity score. A repeated measures analysis employing a restricted maximum likelihood (REML)-based, mixed-effects model approach (MMRM) will be used to analyze the primary efficacy outcome. The MMRM model will include the fixed, categorical effects of treatment group assignment, visit, treatment group-by-visit interaction and pooled site as well as the fixed, continuous covariates of baseline symptom score and the baseline symptom score-by-visit interaction. A detailed description of the MMRM model will be included in the SAP.

In addition to the MMRM model, an analysis of covariance (ANCOVA) model will also be applied. The last-observation-carried-forward (LOCF) will be used to impute any subsequent missing data. The model will have baseline as a covariate, and the fixed, categorical effects of treatment group assignment, pooled site. An observed cases (OC) analysis will also be performed.

As stated previously, any changes in the statistical methods that occur prior to database lock will be documented in the SAP and will not require a protocol amendment.

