
Overall Design:
 
This is a multicenter, randomized, double-blind, placebo-controlled study to be conducted in the United States. Up to eight hundred (800) subjects diagnosed with gastroparesis, who satisfy the selection criteria for the study, will be eligible for one of two groups. Group 1 will enter the Evaluation Phase of the study and Group 2 will enter the Open Label phase of the study. Patients eligible for Group 1 will be randomized to one of two treatment groups. Randomization will be stratified by disease etiology (idiopathic or diabetic), and enrollment for either of the etiologies will be capped at 60% of the total sample size. Patients eligible for Group 2 will enter the Open Label Phase of the study.
 
The study includes two phases: the screening phase and the evaluation phase. The screening phase includes a screening visit to evaluate subjects’ preliminary eligibility for the study. During the screening phase, subjects will collect diary data for at least 4 weeks. The data collected during the screening phase must be reviewed in order to determine eligibility for enrollment into the evaluation phase. Data review will be performed prior or at Visit 2. Patients who to meet all Group 1 eligibility criteria will randomized onto double blind treatment in the evaluation phase. Patients who meet Group 2 criteria or do not meet symptom criteria for randomization but still meet all other eligibility criteria, will be offered open label treatment in the open label arm of the evaluation phase. When enrollment goal is reached for

group 1, group 1 enrollment will be closed and all subsequent patients in screening will be evaluated for group 2 eligibility only.

The Evaluation Phase includes 12 weeks of double blind randomized treatment of placebo or tradipitant (85mg bid, approximately 12 hours apart) for Group 1 or open label tradipitant (85mg bid, approximately 12 hours apart) for Group 2. Daily diaries will be completed during all phases. Clinical evaluations and safety assessments will occur at Screening, Baseline, Week 2, Week 4, Week 6, Week 8, Week 10, and Week 12.

Following the End of Study Visit (Visit 8) patients can opt-in to a one-day optional pharmacokinetic (PK) study where one additional dose of tradipitant will be taken and blood will be drawn pre-dose and, 1, 2, 4, 6, 8-hour post dose to assess drug levels. This optional PK Visit can occur 1-14 days after Visit 8.

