**Sample Size Discussion:**

Based on a two-sided t-test with the 5% significance level, the planned sample size of 100 subjects per arm provides 95% power to detect a mean difference of 0.65 point in the average of daily nausea severity assuming the standard deviation of 1.25 in each treatment group.

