11. STATISTICS

11.1. Sample Size and Accrual

Based on a two-sided t-test with the 5% significance level, the planned sample size of 100 subjects per arm (a total of 200 subjects) provides approximately 98% power to detect a mean difference of 0.65 point in the average of nausea severity score assuming the standard deviation of 1.15 in each treatment group. Assuming an equal enrollment for each of diabetic and idiopathic etiology groups, a total of 100 subjects (50 per arm) per etiology will also provide approximately 80% power for each of these groups.

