11.2. Statistical Methods and Analysis Plan

This section describes the planned statistical analyses in general terms. A complete description of the methodology will be specified in a statistical analysis plan (SAP). Any changes in the statistical methods described in this protocol that occur prior to database lock will be documented in the SAP and will not require a protocol amendment.

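### Randomization is stratified by etiology, but the listed MMRM and ANCOVA terms leave it out, so the test is conservative if etiology is prognostic

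*SAP*

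**What the plan says.** The protocol synopsis (Overall Design) states: "Randomization will be stratified by disease etiology (idiopathic or diabetic", and adds that "enrollment for either of the etiologies will be capped at 60% of the total sample size". No other stratification factor is named. SAP section 11.1 also gives power separately by etiology: "Assuming an equal enrollment for each of diabetic and idiopathic etiology groups, a total of 100 subjects (50 per arm) per etiology", at about 80%.

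SAP section 11.3.1 then lists the model terms. The MMRM has "fixed, categorical effects of treatment group assignment, visit, treatment group-by-visit interaction and pooled site", with baseline score and baseline-by-visit as continuous covariates. The ANCOVA has baseline, treatment and pooled site. Etiology appears in neither. Section 11.3.2 applies a similar analysis to the continuous secondary endpoints, and section 11.5 mentions etiology only among subgroups that may be examined.

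Sections 11.2 and 11.3.1 leave the full model description to a separate statistical analysis plan, which is not among the documents. Etiology may still be added there; the point here is only that the lists as written omit it.

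**The concern.** Stratified 1:1 allocation balances etiology across the arms. Any difference in mean change between idiopathic and diabetic patients therefore drops out of the sampling error of the treatment difference. A model without etiology leaves that variance in its residual, so it reports a standard error larger than the true one. The treatment estimate stays unbiased and type I error falls below 5%. What is lost is precision that the design has already secured, in the form of wider confidence intervals and some power. Pooled site does not stand in for etiology, because sites are pooled for low enrollment.

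All of this is conditional: it matters only if etiology predicts change in nausea beyond baseline score and pooled site.

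**Working it through.** **Inputs from the documents.** 100 per arm, 1:1, two-sided 5% test, difference 0.65. The SD is given twice: the protocol synopsis (Sample Size Discussion) has "assuming the standard deviation of 1.25 in each treatment group" and SAP section 11.1 has "assuming the standard deviation of 1.15 in each treatment group". Both are carried through.

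**The plan's own figures**, by noncentral t:
- SD 1.15, 100 per arm: 97.8% (stated: about 98%)
- SD 1.25, 100 per arm: 95.5% (stated: 95%)
- SD 1.15, 50 per arm: 79.9% (stated: about 80%)

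All three reproduce.

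**Assumed.** The gap g between etiologies in mean change is 0.25, 0.5, 0.8 or 1.0 point. None of these is in the documents, and the last two exceed the planned effect. Also assumed: a 50:50 mix, a single time point, and no baseline or site.

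**Formulas.** With p the share of one etiology, total variance = within-etiology variance + p(1−p)g².
- Reported SE (no etiology) = total SD × √(2/100)
- True SE = within-etiology SD × √(2/100)
- Type I error = P(|t| > critical value × reported SE / true SE), 198 df
- Power from the noncentral t with noncentrality 0.65 / true SE (198 df without etiology, 197 with)

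**One case in full** (SD 1.15 read as the total SD, g = 0.5). Within-etiology variance = 1.3225 − 0.25 × 0.25 = 1.26, so the SD is 1.1225. Reported SE = 1.15 × 0.1414 = 0.1626; true SE = 1.1225 × 0.1414 = 0.1587. The ratio is 1.0245, type I error is 4.5%, and power is 98.1% without etiology against 98.3% with it.

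**All cases** (gaps 0.25 / 0.5 / 0.8 / 1.0):

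| SD and its reading | SE too wide (%) | Type I error (%) | Power without etiology (%) | Power lost (points) |
|---|---|---|---|---|
| 1.15, total | 0.6 / 2.5 / 6.7 / 11 | 4.9 / 4.5 / 3.7 / 3.0 | 97.9 / 98.1 / 98.4 / 98.7 | 0.06 / 0.22 / 0.45 / 0.56 |
| 1.15, within etiology | 0.6 / 2.3 / 5.9 / 9.0 | 4.9 / 4.5 / 3.8 / 3.3 | 97.8 / 97.6 / 97.1 / 96.7 | 0.06 / 0.25 / 0.68 / 1.12 |
| 1.25, total | 0.5 / 2.1 / 5.6 / 9.1 | 4.9 / 4.6 / 3.9 / 3.3 | 95.6 / 95.9 / 96.4 / 96.8 | 0.09 / 0.35 / 0.80 / 1.09 |
| 1.25, within etiology | 0.5 / 2.0 / 5.0 / 7.7 | 4.9 / 4.6 / 4.0 / 3.5 | 95.4 / 95.2 / 94.5 / 93.9 | 0.09 / 0.38 / 1.01 / 1.63 |

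At the 60:40 enrollment cap the effects are slightly smaller (SD 1.15 total: SE 0.6 / 2.3 / 6.4 / 10.5% too wide).

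**Simulation checks at a single time point.**
- 40,000 trials per scenario, SD 1.15 total: null rejection without etiology 5.05 / 4.49 / 3.70 / 2.95%. With etiology it was 4.8 to 5.2% in every scenario.
- ANCOVA with baseline, 10 assumed pooled sites and permuted blocks within etiology. When etiology explained 5% of the variance, null rejection was 4.5 to 4.6% without it and 5.0 to 5.1% with it. At 10% it was 4.1 to 4.2% and 5.1 to 5.2%.

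**Repeated-measures check.** Six post-baseline visits (Weeks 2 to 12) with the section 11.3.1 terms and unstructured covariance, 6,000 trials per scenario. Assumed: complete data, 20 equal pooled sites, within-etiology SD 1.15, baseline explaining 20% of within-etiology variance, adjacent-visit residual correlation 0.7. Week 12 model SE:

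| Etiology gap | As listed | Plus etiology | Plus etiology-by-visit |
|---|---|---|---|
| None | 0.150 | 0.150 | 0.150 |
| Constant 1.0 | 0.167 | 0.150 | 0.150 |
| Growing to 0.5 at Week 12 | 0.154 | 0.151 | 0.150 |
| Growing to 0.8 | 0.161 | 0.153 | 0.150 |
| Growing to 1.0 | 0.166 | 0.154 | 0.150 |

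For the gap growing to 1.0, null rejection was 3.0 / 4.3 / 4.9% across the three models, with Monte Carlo error of about 0.3 points. These results rest on a single simulation run.

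**The case against.** Four points can be made for the plan.

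1. Section 11 describes the analyses only in general terms and leaves the full model to a document not supplied here. That is true, and the final model may contain etiology. But section 11.3.1 names the terms of both models explicitly, and a reader would expect the stratification factor among them.

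2. The effect is small at the planned difference. This stands. At gaps up to 0.5 the power loss is under 0.4 points, and a loss above 1 point needs a gap of about 0.8 or more, larger than the treatment effect itself. The loss grows if the true effect is smaller. At an assumed 0.45 with a within-etiology SD of 1.15, power is 77.3% against 78.6% (gap 0.5) and 75.1% against 78.6% (gap 0.8).

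3. Power falls below the stated 95% only if 1.25 is the SD within etiology. An arm contains both etiologies, so the more natural reading is the total SD, and on that reading power stays above 95% at every gap shown. This also stands, and the shortfall should carry little weight.

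4. Etiology-by-visit adds little. In the simulation a main effect recovers most of the precision, and the interaction takes the SE only from at most 0.154 to 0.150. It is a refinement.

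None of these disputes the omission or makes the remedy costly.

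**Conclusion.** The concern holds as a low-cost improvement that should be made. It is not a validity problem. The listed models omit the only named stratification factor, and the consequence is a conservative test if etiology is prognostic beyond baseline and site. For gaps of 0.25 to 1.0 point the reported SE is 0.5% to 11% too wide. Power at 0.65 falls by about 0.1 to 1.1 points (SD 1.15) or 0.1 to 1.6 points (SD 1.25). The low end of those ranges applies if the etiologies respond similarly, and with no gap there is essentially no loss. Every magnitude rests on an assumed gap. The omission and the direction of its effect do not.

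**What to change.** Add etiology as randomized (idiopathic or diabetic) as a fixed categorical effect in the MMRM and the ANCOVA, for the primary and continuous secondary endpoints. In the MMRM also add etiology-by-visit, parallel to the baseline-by-visit term already listed, so that the Week 12 contrast is adjusted for the Week 12 gap. Write this into the separate analysis plan before unblinding, or state there why etiology is left out.

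The cost is one degree of freedom in the ANCOVA. In the MMRM it is one for the main effect plus five for the interaction, six in all, if the six post-baseline visits are the visit levels. The variable is already collected for randomization, and section 11.3.1 allows method changes before database lock without a protocol amendment.
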